1. Introduction

1.1. Background and rationale

Vascular access surveillance by flow volume measurements with dilution techniques during dialysis sessions is the standard of care in the Netherlands. However, there is a large practice variation in surveillance frequency and the threshold to trigger referral for vascular access intervention.

Combined with the limited evidence base supporting the use of access surveillance, this variation in protocols indicates the need for further studies to determine the most effective method for follow-up of the vascular access for hemodialysis.

1.2. Objectives

The FLOW project evaluates the follow-up of the vascular access for hemodialysis. In current clinical care, vascular access flow volume is periodically assessed to detect and treat asymptomatic stenosis. The FLOW project will determine whether it is safe to abandon this practice of active surveillance. Vascular access stenosis will then be treated only when clinical problems of flow dysfunction occur during hemodialysis.

2. Study Methods

2.1. Trial design

It is a double-blind, multicenter randomized controlled trial with a superiority framework and a 1:1 individual participant treatment allocation ratio over two study arms. In the intervention group, only symptomatic vascular access stenosis detected by clinical monitoring are treated, whereas in the comparison group asymptomatic stenosis detected by surveillance are treated as well (current standard of care in the Netherlands). Prevalent hemodialysis patients with a functional arteriovenous vascular access are eligible to participate in the trial. Patients will be followed up for a minimum of 2 years and a maximum of 3 years (follow up will end for all participants when the last included patient has reached a 2 year follow-up period) and will be censored when their mode of renal replacement therapy is changed to kidney transplantation, peritoneal dialysis, or conservative treatment.

2.2. Randomization

Patients will be randomized using a 1:1 individual participant treatment allocation ratio. The data management center will generate the treatment allocation sequence by a random number producing algorithm on a computer. Randomization will be stratified by treatment center and for vascular access type (graft vs fistula). The study coordinator will enroll participants and will be informed of treatment assignment through an online service provided by the data management center.

2.3. Sample size

Sample sizes were estimated for the number of interventions required for each patient-year of dialysis treatment (i.e. the primary outcome), which will be analysed using a general linear model with Poisson distribution and time as off-set variable. In the FLOW project, we aim to detect a difference in the intervention rate of 0.25 per year between study groups in a superiority analysis. This difference is associated with an economically relevant effect of saving approximately 1 million euros per year at a 75% de-implementation rate. The minimal clinically relevant difference in the intervention rate remains to be defined for this core outcome measure, but will likely be greater than 0.25 per year. In the Netherlands, the access-related intervention rate in hemodialysis patients with arteriovenous fistulas and grafts was 1.56 and 3.30 per year, respectively, in a retrospective observation cohort study in 10 dialysis units. As the distribution between fistulas and grafts is approximately 8:1, these figures amount to an average of 1.77 interventions per patient-year in the Netherlands. Since the study includes young hemodialysis patients waiting for kidney transplantation and old hemodialysis patients with limited life expectancy, 20% of participants are expected to leave the study per year before completing the follow-up period. A total follow-up time of 828 patient-years (414 patient-years in each treatment arm) achieves 80% power to detect a 0.25 decrease in the number of interventions per patient-year between the study groups using a two-sided, large-samples z-test of the Poisson event-rate difference at a significance level of 0.05. With a standard follow-up of 2 years and a drop-out rate of 20% per year, this would require a sample size of 518 patients. Implementing a variable follow-up time of a minimum of 2 years and a maximum of 3 years is expected to result in 162 additional patient-years. This corresponds to 101 patients with 2-years of follow-up and a drop-out rate of 20% per year, and therefore leads to a new sample size estimation of 417 patients. An interim analysis for safety requires a sample size of 144 patients (72 in each treatment arm) contributing 1 year of follow-up with an expected event rate of 0.5 events per patient-year to show non-inferiority with regards to access-related serious adverse events at a margin of 0.5 events per patient-year with a power of 90%.

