	Unselected population (... patient-years)	Enrolled population (...patient-years)	Event rate ratio (95% CI)	P
Interventions for flow dysfunction	N	N	... (....)	...
Percutaneous interventions	N	N	... (....)	...
Balloon angioplasty without stent	N	N	... (....)	...
Balloon angioplasty with stent	N	N	... (....)	...
Percutaneous thrombectomy	N	N	... (....)	...
Surgical interventions	N	N	... (....)	...
Open thrombectomy	N	N	... (....)	...
Patch angioplasty	N	N	... (....)	...
Revision of anastomosis	N	N	... (....)	...
New arteriovenous fistula	N	N	... (....)	...
New arteriovenous graft	N	N	... (....)	...
Ligation of arteriovenous fistula	N	N	... (....)	...
Ligation of arteriovenous graft	N	N	... (....)	...
Central venous catheter interventions	N	N	... (....)	...
Catheter insertion	N	N	... (....)	...
Guidewire exchange	N	N	... (....)	...
Catheter removal	N	N	... (....)	...
Other vascular access interventions	N	N	... (....)	...
Repair (pseudo)aneurysm	N	N	... (....)	...
Ligation of accessory vein	N	N	... (....)	...
Embolisation of accessory vein	N	N	... (....)	...
Superficialisation	N	N	... (....)	...
Distal revision and interval ligation	N	N	... (....)	...
Proximalisation of arterial inflow	N	N	... (....)	...
Revision using distal inflow	N	N	... (....)	...
Banding	N	N	... (....)	...
Serious adverse events				
Thrombosis	N	N	... (....)	...
Access abandonment	N	N	... (....)	...

Statistical analysis: Poisson test with time as offset variable.

Figure 2D: Comparison of enrolled patients with unselected hemodialysis population - Survival

Kaplan-Meier survival curve of unselected hemodialysis population and enrolled patients

Statistical analysis: Log rank test

Figure 2E: Patient allocation to study groups

X-axis: time (1-1095 days)

Y-axis: patients (N=375)

The grid is filled with colors: red when allocated to the monitoring group, blue when allocated to the surveillance group, and grey after the end of the study (different shades of grey may be considered for different reasons to end study participation)

Patients will be ordered according the time of shifting between groups to facilitate interpretation (with patients who remained in the monitoring group the entire study duration at the top of the grid, and patients who remained in the surveillance group the entire study duration at the bottom of the grid)

Table 2F: Vascular access dysfunction detected by monitoring and surveillance - Available measurements

	Monitoring		Surveillance	
	N	Follow-up	N	Follow-up

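### Does the cut from 518 to 417 patients rest on an unsupported 162 extra patient-years?

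*SAP*

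**What the plan says.** SAP section 2.3 sizes the trial for a fall of 0.25 interventions per patient-year from a rate of 1.77, "using a two-sided, large-samples z-test of the Poisson event-rate difference at a significance level of 0.05". This gives 828 patient-years for 80% power. On attrition it states that "20% of participants are expected to leave the study per year before completing the follow-up period". It then goes in two steps from patient-years to patients.

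- Fixed follow-up: "With a standard follow-up of 2 years and a drop-out rate of 20% per year, this would require a sample size of 518 patients".
- Variable follow-up: the longer period "is expected to result in 162 additional patient-years". "This corresponds to 101 patients with 2-years of follow-up and a drop-out rate of 20% per year", which "leads to a new sample size estimation of 417 patients".

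Section 2.1 sets the calendar rule behind the extra time: "follow up will end for all participants when the last included patient has reached a 2 year follow-up period". With individual follow-up of two to three years, this implies an accrual window of about one year.

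The shell for Figure 2E (section 6, Tables and Figures) has a filled-in axis label, "Y-axis: patients (N=375". Nothing in the SAP links 375 to 417.

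**The concern.** The whole reduction of 101 patients rests on the figure of 162, and the SAP gives no derivation for it. The natural first check is to read the loss literally as 20% of the starting number leaving each year and to spread accrual evenly over one year. That reading returns the plan's 518, but at 417 patients it gives about 111 extra patient-years, well short of 162.

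A second check needs no assumption about losses in year three. With even accrual the mean extra time is half a year, so 162 from 417 patients requires about 78% of them still in the study at year two. A continuing 20% yearly loss leaves 60% to 67%.

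If 162 were too high, 417 patients would fall short of 828 patient-years and the stated 80% power would be somewhat optimistic. The 375 in Figure 2E adds to the doubt, because if it were the number enrolled, power would be lower again.

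**Working it through.** **Inputs from SAP section 2.3:** rates 1.77 and 1.77 − 0.25 = 1.52; two-sided α 0.05; power 80%; loss 20% per year; 162 extra patient-years. **From section 2.1:** 1:1 allocation and follow-up of two to three years with a common end. **Assumed, because not stated:** even accrual over one year, so extra time is uniform on 0 to 1 year; and four shapes of loss.

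**The plan's own figures**

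- Patient-years per arm: (1.96 + 0.8416)² × (1.77 + 1.52) / 0.25² = 413.2, rounded up to 414, so 828 in total.
- Patient-years per patient over two years with 20% lost: 2 × 0.8 = 1.6. 828 / 1.6 = 517.5, so 518.
- 162 / 1.6 = 101.25, so 101; 518 − 101 = 417.
- Check: 417 × 1.6 + 162 = 829.2 patient-years, power 80.1%.

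Every step follows once 162 is granted.

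**What 417 patients yield under each loss shape**

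Let S(t) be the proportion still in the study at time t. Extra time per patient is the integral of S from 2 to 2 + u, averaged over u uniform on 0 to 1. For linear loss this is the mean of 0.6u − 0.1u², that is 0.3 − 0.0333 = 0.2667. Power is Φ(0.25 / √(3.29 / (PY/2)) − 1.96), with PY the total patient-years.

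| Loss shape | PY per patient, 2 years | N at fixed 2 years | Extra PY at 417 | Total PY at 417 | Power at 417 | N for 828 PY |
|---|---|---|---|---|---|---|
| Linear, 1 − 0.2t | 1.600 | 518 | 111.2 | 778.4 | 77.6% | 444 |
| Compounding, 0.8^t | 1.613 | 513–514 | 124.0 | 796.8 | 78.6% | 434 |
| Constant hazard 0.2 | 1.648 | 502–503 | 130.9 | 818.3 | 79.6% | 422 |
| Flat factor 0.8 | 1.600 | 518 | 166.8 | 834.0 | 80.4% | 414 |

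The linear and flat shapes both give 1.600 patient-years over two years, so the plan's 518 cannot tell them apart.

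**Retention needed for exactly 162.** With even accrual and no loss after year two, 162 / (417 × 0.5) = 77.7% must remain at year two. Linear loss leaves 60%, compounding 64% and constant hazard 67%. This tests the figure 162 under even accrual. It does not test the power claim.

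**Other ways to reach 162**

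- Earlier-weighted accrual: under linear loss, an equal extra time x per patient must satisfy 0.6x − 0.1x² = 162/417 = 0.3885, so x ≈ 0.74 year. This lies within the one-year window.
- A different base number: constant hazard applied to 518 patients gives 518 × 0.3139 = 162.6. The SAP does not confirm that this was the source. If it was, the gain includes patients who were then removed, and the constant-hazard row applies: 130.9 extra and 79.6% power.

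**If 375 were the enrolled number.** Total patient-years would be 375 × 1.8667 = 700 (linear) to 375 × 2.0 = 750 (flat), with power 73.2% to 76.1%.

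**The case for a change.** The best argument for changing the text is that a reader cannot check 162. The loss is expressed as a yearly rate each time it appears, and linear loss is its most literal reading. None of the four models with even accrual gives exactly 162 at 417 patients, and the constant-hazard match at 518 suggests that the gain may have been credited to the wrong number of patients. A sentence giving the accrual and loss assumptions would settle this at no cost, and another could say what 375 stands for.

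Part of this stands. The derivation is not shown, the base number is not given, and 375 is not explained. It does not follow that the plan is wrong. The yearly rate is stated and the accrual window is implied; only the shapes are missing, and working of that kind is often kept outside an SAP. Linear loss is a choice made by the reader and is the least favourable of the four. The flat factor fits 518 equally well and supports 417. Constant hazard fails to give 162 at 417, yet still leaves power at about 80%.

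As for 375, a footnote to the monitoring tables (2F to 2H) mentions data problems from November 2024 onwards, so the document was edited with the trial under way. The label may therefore be the enrolled number, though this is unconfirmed. Enrolling fewer than planned would not be an inconsistency in the plan.

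**Conclusion.** The concern does not call for a change. Section 2.3 leaves out how 162 was obtained, but its other steps reproduce. With even accrual over one year, 417 patients give power between 77.6% and 80.4%, depending on a loss shape the SAP leaves open. The largest shortfall from 80% is about 2.4 percentage points, and it disappears under a flat 20% cut, which agrees with the plan's own 518. Stating the assumptions would make the paragraph easier to follow. It would not alter the target, the primary model, any estimate or any decision rule, and the stated power might not move at all. The 375 in Figure 2E is an unexplained label in a figure shell, and the 73% to 76% power attached to it depends on a guess about what it means. These conclusions rest on the planning rates of 1.77 and 1.52 and on the Poisson variance used in the plan's own calculation.

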2.4. Framework

Superiority framework. The intervention group will be compared to the control group. Analyses will be stratified for treatment center and for vascular access type (graft vs fistula). Every effort is made to establish eligibility of participants prior to randomization; no withdrawals due to ineligibility are allowed and the analyses include all participants enrolled. The primary analysis will be on the intention to treat population (i.e. no participants are withdrawn from analysis for lack of adherence to treatment allocation); exploratory on-treatment analyses will be performed. A comparison of included and excluded patients is done to provide insight into the external validity of the clinical trial. Every effort is made to avoid missing data, including assistance from dialysis nurses in obtaining patient-reported outcome measures during dialysis sessions. Primary outcome data are not expected to be missing, as interventions on vascular access will be reported in the patients' medical files. We expect no loss to follow-up in the study participants since they are observed three times per week in the dialysis unit. Patient-reported outcomes will be analysed using generalized estimating equations that allow for missing data. Other missing data will be handled by using 5 imputation cycles with regression methods. Outliers will not be removed from the analysis unless the data can clearly be shown to be erroneous.

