2.7. Timing of outcome assessments

Physical examination of the vascular access will be done at each dialysis session. Volume measurements by ultrasound dilution will be done every month. Duplex ultrasound examination of the vascular access will take place in case of flow dysfunction, and interventions for flow dysfunction are part of standard clinical care for hemodialysis patients. Subjects enrolled in the trial will be asked to fill out questionnaires (SF-VAQ, EQ-5D-5L, MCQ and PCQ) at baseline and every 3 months until 24 months of follow up.

3. Statistical Principles

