- SF-VAQ measured at baseline and every 3 months during the follow-up period. The Short-Form Vascular Access Questionnaire (SF-VAQ) was developed to measure hemodialysis patients' satisfaction with their vascular access (31). The questionnaire contains 13 items (7-point Likert scale) in 4 domains (overall satisfaction, physical symptoms, social functioning and complications), and has a single summary score.

- EQ-5D-5L measured at baseline and every 3 months during the follow-up period. The EQ-5D-5L was developed to measure health-state utility values. The questionnaire contains self-classifiers at 5 levels in 5 dimensions (mobility, self-care, usual activities, pain/discomfort and anxiety/depression) (32). Utility values will be calculated from these health states using preferences elicited from the Dutch general population (36). Quality-adjusted life years will be calculated with these utility values using the area under the curve method.

6. Quality of the surveillance program

- Repeatability and reproducibility of vascular access flow volume measurements (mL/min) using ultrasound dilution in routine clinical practice.
- Diagnostic accuracy of vascular access flow volume measurements to predict clinical signs of flow dysfunction and access thrombosis within 1 month in the intervention group. Diagnostic accuracy will be reported as sensitivity, specificity, negative predictive value, and positive predictive value.
- The percentage of vascular access balloon angioplasties that have resulted in technical success (residual stenosis <30%) and clinical success (increase in flow volume to >500mL/min, restoration of vascular access function and resolution of any clinical signs of flow dysfunction).
- Vascular access primary, primary assisted, and secondary patency after balloon angioplasty (time to event).
- Adherence (in %) to the vascular access follow-up protocol and to the study protocol for referral to correct vascular access stenosis.

7. Other outcome measures will be registered for explanatory analyses and are defined according to the ESVS guidelines on vascular access (1):

- Primary patency of vascular access (intervention-free vascular access survival): the interval (in days) between randomization and the first intervention for vascular access dysfunction or thrombosis or its abandonment.

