Stratification for study site and vascular access type (fistula / graft).

Subgroup analysis: vascular access type (fistula / graft).

Sensitivity analysis:

- Exclusion of patients with interventions with technical failure (see Table 7A)
- Exclusion of patients with interventions with clinical failure (see Table 7A)

Table 4B: Access-related adverse events

	Monitoring (... patient-years)	Surveillance (...patient-years)	Event rate ratio (95% CI)	P
Access-related adverse events	N	N	... (....)	...
Pain requiring medication (days)	N	N	... (....)	...
Infection requiring antibiotics (days)	N	N	... (....)	...
Bleeding requiring blood transfusion	N	N	... (....)	...
Central venous catheter thrombolysis	N	N	... (....)	...

Statistical analysis (intention to treat population): general linear mixed effect model with Poisson distribution and identity link, and with time as off-set variable (see Table 3A for details).

Table 4C: Hospital admittance

	Monitoring (...patient-years)	Surveillance (...patient-years)	Event rate ratio (95% CI)	P
Hospital admittance (days)	N	N	... (...-...)	...
Related to vascular access	N	N	... (...-...)	...
Unrelated to vascular access	N	N	... (...-...)	...

Statistical analysis (intention to treat population): general linear mixed effect model with Poisson distribution and identity link, and with time as off-set variable (see Table 3A for details).

Table 4D: Line listing of serious adverse events

Table 4E: Line listing of protocol deviations

Table 5A: SF-VAQ scores at baseline

	All patients (N=...)	Monitoring (N=...)	Surveillance (N=...)	P
Total score
Physical domain
Pain
Bleeding
Swelling
Bruising
Social functioning domain
Daily activities
Appearance
Sleep
Bathing and showering
Dialysis complications domain
Problem on dialysis
Access care
Hospitalization
Worry about access longevity

Groups are based on initial randomization

Include only questionnaires with complete data. Questions are Likert scores from 1 to 7. Domain scores are the sum of the 4 questions. The total score is the sum of the 3 domains.

Statistical analysis: Students t-test.

Table 5B: SF-VAQ scores according to the number of interventions during follow-up

	No interventions during follow-up (N=...)	1 intervention during follow-up (N=...)	>1 intervention during follow-up (N=...)	P
Total score
Physical domain
Pain
Bleeding
Swelling
Bruising
Social functioning domain
Daily activities
Appearance
Sleep
Bathing and showering
Dialysis complications domain

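### Baseline SF-VAQ and EQ-5D-5L scores are collected, but no adjustment for them is prespecified in the GEE or in any between-arm QALY comparison

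*SAP*

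**What the plan says.** Section 5.1.2, item 5, sets the schedule for both instruments: "SF-VAQ measured at baseline and every 3 months during the follow-up period" and "EQ-5D-5L measured at baseline and every 3 months during the follow-up period". Section 2.7 has the questionnaires filled out "at baseline and every 3 months until 24 months of follow up", which makes one baseline and eight follow-up visits.

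The between-arm analysis is one sentence in section 2.4, repeated in 5.3: "Patient-reported outcomes will be analysed using generalized estimating equations that allow for missing data". It names no covariates, time terms or contrast, and does not say whether the baseline score is a covariate or one of the repeated outcomes. Section 2.4 also says in general terms that analyses are stratified for centre and access type. Section 5.2.2 covers serious adverse events, complications and thrombosis, and does not mention questionnaires.

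For utilities, section 5.1.2 says: "Quality-adjusted life years will be calculated with these utility values using the area under the curve method". No model for comparing QALYs between arms follows.

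Among the table shells, baseline SF-VAQ is compared by arm in Table 5A ("Statistical analysis: Students t-test") and serves as the outcome of a predictor model in Table 5E. Tables 5B to 5D compare scores by number of interventions or before and after an event. None compares follow-up scores by arm.

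**The concern.** A patient's own starting score usually predicts that patient's later scores on the same scale. Leaving it out of the model leaves explainable variation in the error term and widens the intervals. A t-test of baseline scores by arm does not remove that variation or correct an imbalance.

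The issue is sharper for QALYs. Baseline utility is the first point of the area under the curve and is correlated with every later point. An arm that starts higher by chance will therefore tend to accrue more QALYs without any treatment effect, and that difference would be read next to the cost outcome.

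Leaving the choice open also means that it could be made after the data have been seen.

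**Working it through.** **Inputs from the SAP.** Visits at 0, 3, …, 24 months (2.7); 1:1 allocation (2.2); planned N = 417 (2.3). The SAP states no SD, correlation, power or precision for SF-VAQ, EQ-5D-5L or QALYs, so there is no figure to reproduce.

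**Assumptions, not in the SAP.** Within-patient correlation ρ from 0.3 to 0.7, equal between all visits (exchangeable); complete data; one allocation per patient throughout; utility SD 0.20 to 0.30.

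**1. Time-averaged questionnaire contrast.** In units of SD², the per-patient variance of the mean of eight follow-up scores is (1 + 7ρ)/8. With the baseline score as covariate it falls by ρ².

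| ρ | Unadjusted | Adjusted | Reduction |
|---|---|---|---|
| 0.3 | 0.3875 | 0.2975 | 23% |
| 0.5 | 0.5625 | 0.3125 | 44% |
| 0.7 | 0.7375 | 0.2475 | 66% |

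**2. QALY contrast.** The trapezoid weights over 2 years are 0.125 at each end and 0.25 at the seven visits between (sum 2.0). The sum of squared weights is 2 × 0.125² + 7 × 0.25² = 0.46875.
- Var(AUC)/SD² = 0.46875(1 − ρ) + 4ρ.
- Slope of AUC on baseline utility: c = 0.125 + 1.875ρ.
- Adjusted variance = Var(AUC) − c².

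| ρ | Var(AUC) | c | c as share of 2.0 | Reduction = c²/Var(AUC) |
|---|---|---|---|---|
| 0.3 | 1.528 | 0.688 | 34% | 31% |
| 0.5 | 2.234 | 1.063 | 53% | 51% |
| 0.7 | 2.941 | 1.438 | 72% | 70% |

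The baseline point's direct weight is only 0.125/2 = 6.25%. The rest of the pass-through comes from correlation with later visits.

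**3. Sensitivity to the correlation pattern.** With exponential decay and ρ set at 12 months, the reductions are 20%, 37% and 58% for the questionnaire contrast, and 28%, 44% and 64% for QALYs. The pass-through is 38%, 54% and 72%.

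**4. Size of a typical imbalance.** The SE of a chance baseline difference is SD × 2/√417 = 0.098 SD. At SD 0.25 that is 0.0245 in utility. Multiplied by c, a 1-SE imbalance moves the 2-year QALY contrast by 0.017, 0.026 or 0.035 at ρ = 0.3, 0.5 or 0.7. Over SD 0.20 to 0.30 the range is 0.014 to 0.042. Figure 2E shows N = 375, which raises the SE to 0.103 SD and the shifts by about 5%.

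**5. Simulation.** In 4,000 trials of 208 per arm (SD 0.25, exchangeable, ρ = 0.5), the SE of the QALY contrast fell from 0.0362 to 0.0258 with adjustment. Its slope on the baseline difference fell from 1.06 to −0.005. At ρ = 0.7 the SE fell from 0.0428 to 0.0229 and the slope from 1.45 to 0.01. With no true effect, the mean unadjusted contrast was 0.0002 and 0.0012, so it is unbiased over repeated randomizations.

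**The case against.** - **The SAP is silent; it does not say that the analysis is unadjusted.** This stands. A reader might infer that the plan has chosen an unadjusted analysis, but the text only leaves the covariates open. A GEE with baseline among the repeated outcomes and an arm-by-time term would also take account of baseline. The choice still matters. With a free arm difference at baseline, that contrast is a change from baseline, with variance (1 + 7ρ)/8 + 1 − 2ρ. This gives 0.7875, 0.5625 and 0.3375 at ρ = 0.3, 0.5 and 0.7, against 0.2975, 0.3125 and 0.2475 with the covariate.
- **No between-arm QALY analysis is given, and an economic analysis may sit in another plan.** The first part stands, so the QALY finding is conditional on such a comparison being made. QALYs are nevertheless described among this SAP's outcomes, and section 3.1 says that inferential techniques will be discussed in later sections of the SAP.
- **Patients may change arm.** Figure 2E refers to patients shifting between groups, and Table 2L to a subsequent randomization after an intervention. The figures above assume one allocation per patient and do not carry over unchanged. This stands and shapes the fix.
- **Complete data are assumed, although section 2.3 expects 20% to leave per year.** This stands; the percentages are indicative. Nor can a gain in power be attributed to this trial, because the SAP makes no power claim for these outcomes.
- **These are secondary outcomes.** This stands; it limits the weight of the point but does not remove it.

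**Conclusion.** The point holds as a gap in prespecification that costs precision on secondary outcomes. Under exchangeable ρ of 0.3 to 0.7, complete data and fixed allocation, baseline adjustment would cut variance by about 23% to 66% for the time-averaged SF-VAQ or EQ-5D-5L contrast and by about 31% to 70% for a 2-year QALY contrast. The reductions are somewhat smaller if correlation decays with time.

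A reader might infer that a chance baseline difference passes in full into the QALY result, or that the result is biased. Neither follows. The pass-through is about 34% to 72% of the full 2-year effect, and the unadjusted contrast is unbiased over repeated randomizations. What is at issue is imbalance in the one sample that is realised. The primary analysis is not touched.

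**What to change.** In sections 2.4 and 5.3, and in a new paragraph on patient-reported outcomes in 5.2.2, state the following:

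1. The SF-VAQ and EQ-5D-5L GEEs use follow-up scores only as outcomes, with the enrolment baseline score of the same instrument, study site and access type as covariates.
2. Any between-arm QALY comparison is a regression that includes enrolment baseline utility and the stratification factors.
3. To which allocation follow-up scores and QALYs are attributed when a patient is randomized again or shifts between groups.
4. How a missing baseline questionnaire is handled. The existing rule does not cover it: sections 2.4 and 5.3 assign patient-reported outcomes to the GEE and reserve regression imputation for other missing data.

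The data are already collected, so no new measurement is needed. Items 1 and 2 take a sentence each. Items 3 and 4 need a decision and a short rule, preferably before the arms are compared.
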